### 5.6. Safety Evaluation

All safety analyses will be performed using the TS except otherwise specified.

CONFIDENTIAL	STATISTICAL ANALYSIS PLAN N° LUF-44-001  VERSION N° 2.0	Page 17 / 29
	DATED: JUNE 30, 2021	

### 5.6.1. Extent of Exposure

Extent of exposure will be summarized per subject, per procedure and if necessary, per administration (e.g. injection). The following parameters will be tabulated:

Per subject:

- Duration between first Study Procedure and “ICF signature” (in days, calculated as the difference between the date of “First Study Procedure” and “ICF signature”),
- Duration of subject’s participation (in days, calculated as the difference between the date of “End of study” and “ICF signature”),
- Number of procedures (presented as quantitative and categorical data [Only one procedure/2 procedures]),
- Number of subjects having a second procedure during the study (number of subjects and percent [n row / N subjects] \* 100]),
- Reason for having a second procedure (number of subjects and percent [n row / N subjects having a second procedure] \* 100]),
- Summary statistics (number [n], mean, standard deviation [SD], median, minimum, and maximum) on the time interval (in days) between second and first study procedure.

Per subject and per procedure:

- Number of injections (presented as quantitative and categorical data [Only one injection/2/3/4/5/6 injections]),
- Punctures sites (number and % of subjects),
- Glues brand name (number and % of subjects),
- Duration of the procedure (in minutes, calculated as the difference between “Time leaving the catheterization laboratory” and “Time of first injection”).

Per subject, procedure and injection:

- Total volume and ratio of mixture,
- Volumes of Lipiodol® Ultra Fluid and of the glues will be calculated,
- Catheter flush done.

Per subject, procedure and lesion:

- Number of lesions treated (presented as quantitative and categorical data [Only one lesion/2 lesions/3 lesions/4 lesions]),
- Other embolization material used,
- Type of embolization material.

Listing of exposure will be presented in CSR appendix 16.2.7.

### 5.6.2. Adverse Events

Adverse events (AEs) will be coded in System Organ Class (SOC) and Preferred term (PT) using the Medical Dictionary for Regulatory Activities (MedDRA) latest version in force at the date of data base lock.

AEs with missing relationship will be considered related to the mixture (except if date of onset is before date of first procedure) and to the study procedure.

#### 5.6.2.1 Primary analysis of the primary criteria

The following parameters will be described on ADRs occurring, per study procedure, after administration of Lipiodol® Ultra Fluid in association with surgical glues and before catheterization laboratory discharge (i.e

CONFIDENTIAL	STATISTICAL ANALYSIS PLAN N° LUF-44-001  VERSION N° 2.0	Page 18 / 29
--------------	---	--------------

ADR start date is greater or equal to time of first injection and lower or equal to time leaving the catheterization laboratory):

- Number and percentage of subjects experiencing at least one ADR,
- Number of ADRs,
- Distribution of number of ADRs per subject (1/2/3 or more),
- Number and percentage of subjects presenting with at least one ADR per intensity,
- Number of ADRs according to their intensity,
- Number and percentage of subjects presenting with at least one ADR per outcome,
- Number of ADRs according to their outcome,
- Number and percentage of subjects presenting with at least one ADR requiring an ADR-targeted medication,
- Number of ADRs requiring an ADR-targeted medication,
- Number and percentage of subjects presenting with at least one ADR requiring another ADR-targeted action,
- Number of ADRs requiring another ADR-targeted action,
- Number and percentage of subjects presenting with at least one ADR per lesion location,
- Number of ADRs per lesion location,
- Number and percentage of subjects presenting with at least one ADR per lesion type,
- Number of ADRs per lesion type,
- Number and percentage of subjects with mixture administration withdrawal due to at least one ADR,
- Number of ADRs leading to discontinuation of mixture administration,
- Number of ADRs leading to premature discontinuation,
- Number and percentage of subjects presenting with at least one serious ADR, whatever the seriousness criteria,
- Number of serious ADRs, whatever the seriousness criteria,
- Number and percentage of subjects presenting with at least one serious ADR per seriousness criteria,
- Number of serious ADRs per seriousness criteria.

The following distributions, by SOC and PT, will be tabulated on ADRs occurring, per study procedure, after administration of Lipiodol® Ultra Fluid in association with surgical glues and before catheterization laboratory discharge (i.e ADR start date is greater or equal to time of first injection and lower or equal to time leaving the catheterization laboratory):

- Number and percentage of subjects experiencing at least one ADR and number of ADRs,
- Number and percentage of subjects experiencing at least one ADR requiring an ADR-targeted medication and number of ADRs,
- Number and percentage of subjects experiencing at least one ADR requiring another ADR-targeted action and number of ADRs,
- Number and percentage of subjects experiencing at least one ADR leading to discontinuation of mixture administration and number of ADRs,
- Number and percentage of subjects experiencing at least one serious ADR and number of serious ADRs.

Parameters and distributions will also be presented according to the surgical glue (Histoacryl®, Endoacryl®, Other) associated to Lipiodol® Ultra Fluid.

#### 5.6.2.2 *Supportive analyses of primary criterion*

None.

#### 5.6.2.3 *Additional analyses of primary criterion*

None.

CONFIDENTIAL	STATISTICAL ANALYSIS PLAN N° LUF-44-001  VERSION N° 2.0	Page 19 / 29
--------------	---	--------------

#### 5.6.2.4 *Analysis of secondary criteria*

The primary analysis of the primary criteria will be repeated with all ADRs occurring between catheterization laboratory discharge (the last one, if applicable) and end of follow-up period (see 5.6.2.1). The same analysis will be performed with all ADRs occurring from the first administration of the mixture up to the end of follow-up period. (see also 5.6.2.1).

Moreover, the following parameters will be described on AEs occurring, per study procedure, after administration of Lipiodol® Ultra Fluid in association with surgical glues and before catheterization laboratory discharge:

- Number and percentage of subjects experiencing at least one AE,
- Number of AEs,
- Distribution of number of AEs per subject (1/2/3 or more),
- Number and percentage of subjects presenting with at least one AE per intensity,
- Number of AEs according to their intensity,
- Number and percentage of subjects presenting with at least one AE per outcome,
- Number of AEs according to their outcome,
- Number and percentage of subjects presenting with at least one AE requiring an AE-targeted medication,
- Number of AEs requiring an AE-targeted medication,
- Number and percentage of subjects presenting with at least one AE requiring another AE-targeted action,
- Number of AEs requiring another AE-targeted action,
- Number and percentage of subjects experiencing at least one AE leading to discontinuation of mixture administration,
- Number of AEs leading to discontinuation of mixture administration,
- Number of AEs leading to premature discontinuation,
- Number and percentage of subjects presenting with at least one AE related to the mixture (ADR), at least one AE related to the study procedure and at least one AE related to the mixture and related to study procedure,
- Number of AEs related to the mixture (ADR), related to the study procedure and related to the mixture and to study procedure,
- Number and percentage of subjects presenting with at least one serious AE, whatever the seriousness criteria,
- Number of serious AEs, whatever the seriousness criteria,
- Number and percentage of subjects presenting with at least one serious AE per seriousness criteria,
- Number of serious AEs per seriousness criteria.

The following distributions, by SOC and PT, will be tabulated on AEs occurring, per study procedure, after administration of Lipiodol® Ultra Fluid in association with surgical glues and before catheterization laboratory discharge:

- Number and percentage of subjects experiencing at least one AE and number of AEs,
- Number and percentage of subjects experiencing at least one AE requiring an AE-targeted medication and number of AEs,
- Number and percentage of subjects experiencing at least one AE requiring another AE-targeted action and number of AEs,
- Number and percentage of subjects experiencing at least one AE leading to discontinuation of mixture administration and number of AEs,
- Number and percentage of subjects experiencing at least one AE related to the study procedure and number of AEs,

CONFIDENTIAL	STATISTICAL ANALYSIS PLAN N° LUF-44-001  VERSION N° 2.0	Page 20 / 29
--------------	---	--------------

- Number and percentage of subjects experiencing at least one AE related to the mixture and to study procedure and number of AEs,
- Number and percentage of subjects experiencing at least one serious AE and number of serious AEs.

The same analyses will be performed, on one hand, on all AEs occurring between catheterization laboratory discharge (the last one, if applicable) and end of follow-up period and on all AEs occurring from the first administration of the mixture up to the end of follow-up period, on the other hand.

Data listings will present all AEs reported, including AEs occurring between date of ICF signature and date of first procedure (ICF date  $\leq$  AEs onset date  $<$  1st procedure date). Adverse event listings will be sorted by site and subject number and will display also the study procedure, surgical glue, puncture site, body system, and preferred term, time of onset (by convention, from the time of the first injection), duration, intensity, seriousness, outcome, action taken and causal relationship to IMP/procedure (presented in CSR appendix 16.2.7).

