### 7.2 Secondary Criteria

The study will evaluate additional safety criteria:

- ADRs from the first administration of Lipiodol® Ultra Fluid in association with surgical glues up to the end of the follow-up period.
- The complete set of AEs collected during the study, regardless of causal relationship assessments, from written informed consent until end of the follow-up period.

Efficacy will be explored with the following assessments:

- Target obliteration per lesion evaluated before the first procedure according to 4 level-score: 1. <50%; 2. 50-75%; 3. 75-99%; and 4. 100% corresponding to a complete nidus obliteration rate
- Post-procedure obliteration per lesion will be evaluated after each procedure according to the same 4 level-obliteration-score
- Successful lesions embolization, expressed as the lesions achieving the targeted percentage of obliteration

At subject enrolment visit, all lesions designated for vascular embolization using Lipiodol® Ultra Fluid associated with surgical glue will be described on the basis of the most recent angiogram and will be associated to a target percent obliteration (i.e. at least x% obliteration or approximately x% obliteration) that is expected to be reached during the procedure. After the procedure, the percent obliteration will be assessed on earliest available angiogram (e.g. Digital Subtraction Angiography (DSA), Computerized Tomography-Angiography (CTA), Magnetic Resonance Angiography (MRA), vascular imaging Ultrasound (US), Doppler US) consistence with the target obliteration will be provided by the investigator.

Guerbet    CONFIDENTIAL	Protocol No. LUF-44-001 Version No. 3.0 Date January 20 th 2017	Page 23 / 43
--	--	--------------

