### 9.2 First Study procedure

The study procedure is a vascular embolization using Lipiodol® Ultra Fluid in association with surgical glue (the mixture) via selective arterial catheterization.

Site staff will collect the following information related to the first study procedure:

- The conditions of mixture administration: date of the procedure, time of first injection of the mixture, associated surgical glue (brand name), puncture site, time leaving the catheterization laboratory, number of injections, and per injection : concerned lesion, ID number of IMP, mixture ratio of Lipiodol® Ultra Fluid to surgical glue, total volume, catheter flush if any (yes/no)
- Changes in therapeutic/palliative strategy introducing additional embolization material
- Post-procedure obliteration (evaluated according to 4 level-score: 1. <50%; 2. 50-75%; 3. 75-99%; and 4. 100% corresponding to a complete nidus obliteration rate) per lesion assessed on

 CONFIDENTIAL	Protocol No. LUF-44-001 Version No. 3.0 Date January 20 th 2017	Page 25 / 43
---	--	--------------

earliest available angiogram after the first embolization procedure (e.g. DSA, CTA, MRA, US, Doppler US)

- Safety information: adverse event(s), whether serious or not. For more information on safety reporting, refer to Section 10
- Concomitant medications

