#### 10.1.3 Description of Adverse Events

The following guidelines and definitions should be used by the investigator for the description of an AE when reporting information:

- **Nature of AE:** preferably an overall diagnosis or syndrome, rather than individual symptoms or signs. The investigator must report AE using standard medical terminology. The same terms should be used in the source documentation and in the CRF.
- **Date and time of onset:** date and clock time of the AE start
- **Intensity:**
  - Mild: the subject is aware of the sign or symptom, but it does not interfere with her/his usual daily activities and/or it is of no clinical consequence

- Moderate: the AE interferes with the usual daily activities of the subject or it is of some clinical consequence
- Severe: the subject is unable to work normally or to carry out his/her usual daily activities, and/or AE is of definite clinical consequence.
- **Date of the event end** (or consolidation): The real date of event end will be entered if the event has come to its end before the date of end of subject's follow-up. If the AE is still ongoing by the time of end of study follow-up for the subject, the subject should be followed-up until AE resolution or a justification should be provided by the Investigator (e.g. chronic disease or subject lost to follow-up) in the medical file.
- **Causal relationship to the mixture of Lipiodol® Ultra Fluid and surgical glue :**
  - Related: the definition of adverse reaction implies a reasonable possibility of a causal relationship between the event and the mixture. This means that there are facts (evidence) or arguments to suggest a causal relationship.
  - Not related: Applicable when no mixture has been administered (pre-administration period) or when no causal relationship exists between the mixture and the event, but an obvious alternative cause exists (e.g. the subject's underlying medical condition or concomitant therapy).

All AEs assessed as related to the mixture will qualify as ADRs in the evaluation of primary and secondary criteria, as described in section 7.
- **Causal relationship to the study procedure of vascular embolization :**
  - Related
  - Not related
- **Outcome:**
  - Recovered/Resolved: the AE is no longer present at any intensity.
  - Recovered/Resolved with sequelae: the AE is resolved but residual effects are still present.
  - Not recovered/Not Resolved: the AE is still present at the last contact with the subject.

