### 12.3 Safety Data

**Extent of exposure data** will be summarized per patient, per procedure and if necessary per administration: Number of procedures, reason for having a second procedure, subject duration of participation, number of injections, total volume and ratio of mixture, volumes of Lipiodol® Ultra Fluid and of the glues will be calculated, glues brand name, punctures sites, catheter flush done, other embolization material used and duration from first injection up to the time leaving the catheterization laboratory.

**Concomitant medication, material and procedures** administered during the subject participation will be summarized: Concomitant medications, additional embolization material introduced during study procedures and any new therapeutic/palliative procedure reported at follow-up will be

 CONFIDENTIAL	Protocol No. LUF-44-001 Version No. 3.0 Date January 20 th 2017	Page 34 / 43
---	--	--------------

summarized. Concomitant medications will be coded using the WHODrug dictionary and tabulated by ATC codes.

**Safety variables** collected for this study are the following; descriptive statistics will be performed on these data.

For the primary evaluation criterion, the following parameters will be described on adverse events related to the mixture (ADRs) occurring per study procedure(s):

- Number and percentage of subjects experiencing at least one ADR
- Number and percentage of ADRs
- Number and percentage of subjects experiencing at least one serious ADR
- Distribution by System Organ Class and preferred term (MedDRA Dictionary): number and percentage of subjects experiencing at least one ADRs and number and percentage of ADRs
- Number and percentage of ADRs according to their intensity and outcome
- Number and percentage of subjects treated for an ADR
- Number and percentage of subjects with mixture administration withdrawal due to ADRs

For the secondary evaluation criterion, ADRs descriptions will be repeated with all ADRs occurring in the whole subject participation period (Study procedure (s) and follow-up period).

Adverse events parameters will be collected as described in section [10.1.3](#) during the study procedure(s) and during the follow-up period.

For the secondary evaluation criteria related to AEs, all parameters will be described (secondary safety criteria):

- Number and percentage of AEs
- Number and percentage of subjects experiencing at least one AE

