- Distribution by System Organ Class and preferred term (MedDRA Dictionary): number and percentage of subjects experiencing at least one SAEs and number and percentage of SAEs
- Distribution by System Organ Class and preferred term (MedDRA Dictionary): number and percentage of subjects experiencing at least one AEs and number and percentage of AEs
- Number and percentage of AEs according to their intensity, outcome, action taken (with IMP and other)
- Number and percentage of AEs related to the mixture (ADRs), AEs related to study procedure and AEs both related to the mixture and related to study procedure.
- Number and percentage of subjects treated for an AE
- Number and percentage of subjects with mixture administration withdrawal due to an AE

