#### 2.3.2. Secondary Safety Criteria

Secondary criteria included to support the primary endpoint are the following:

- ADRs from the first administration of Lipiodol® Ultra Fluid in association with surgical glues up to the end of follow-up period,
- The complete set of AEs collected during the study, regardless of causal relationship assessments, from written informed consent until end of the follow-up period.

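### The secondary AE criterion runs from informed consent, but no AE table visible in SAP 5.6.2.4 opens before the first mixture administration, so earlier AEs are listed and not counted

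*SAP*

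**What the plan says.** SAP 2.3.2 states the criterion as "The complete set of AEs collected during the study, regardless of causal relationship assessments, from written informed consent until end of the follow-up period". Protocol 7.2 gives the same period, "from written informed consent until end of the follow-up period".

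SAP 5.6.2.4 then sets three windows for the AE tables:

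- per procedure, from administration of the mixture to leaving the catheterization laboratory;
- from the last laboratory discharge to the end of follow-up;
- the widest, "on all AEs occurring from the first administration of the mixture up to the end of follow-up period".

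The same section sends all reported AEs to data listings and names those with onset between consent and the day before the first procedure. SAP 5.6.3 lists deaths and serious AEs separately.

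Protocol 12.3 is narrower than 7.2 on timing: it speaks of AE parameters collected "during the study procedure(s) and during the follow-up period". It also plans numbers and percentages of "AEs related to study procedure and AEs both related to the mixture and related to study procedure", and SAP 5.6.2.4 has rows for these. Protocol 10.1.3 records causality to the procedure separately from causality to the mixture, and treats an AE before any mixture is given as unrelated to the mixture.

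**The concern.** Consent defines the start of the criterion, while the first administration defines the start of every visible table. A reader of the report who takes the widest AE table as the result for the SAP 2.3.2 criterion would be reading a shorter period than the one defined.

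The pre-procedure days matter little for judging the mixture. The hours on the table before the first injection matter more. Arterial access and catheterization come before the injection, and a complication at that stage can be related to the study procedure even though it cannot be related to the mixture. The rows for procedure-related AEs are where a reader would look for it.

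**Working it through.** The documents give no figure to reproduce here; 125 is a regulatory requirement. The check compares windows.

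**1. Length of the periods.** Inputs: up to 7 days from enrolment to the first procedure, up to 30 days to an optional second, and follow-up at 30 +/- 3 days (Protocol 3.2 and 9).

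- Criterion: 7 + 30 + 33 = 70 days, which agrees with the stated maximum of 70.
- Widest AE table: 30 + 33 = 63 days.
- Not tabulated: 70 - 63 = 7 days at most, plus any pre-injection part of the first procedure day.

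**2. Example onset times against the three windows.** The per-procedure window is taken to open at the time of the first injection, as SAP 5.6.2.1 defines it for ADRs.

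| AE onset | Administration to lab discharge | Last discharge to end of follow-up | First administration to end of follow-up |
|---|---|---|---|
| 3 days before procedure 1 | no | no | no |
| 0.5 h before first injection, procedure 1 | no | no | no by clock time; yes by date |
| During procedure 1, after injection | yes | no | yes |
| Between procedures | no | no | yes |
| 0.5 h before first injection, procedure 2 | no | no | yes |
| During procedure 2, after injection | yes | no | yes |
| Follow-up | no | yes | yes |

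The first row is uncounted on any reading. The second depends on a rule that the SAP does not give.

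**3. Date or clock time?** SAP 5.6.2.1 compares ADR onset with the time of injection, and the listings in 5.6.2.4 time onset from the first injection; both point to clock time. The missing-relationship rule in SAP 5.6.2 and the pre-procedure interval named for the listings both use dates. Either rule can be programmed: Protocol 10.1.3 collects "date and clock time of the AE start", and Protocol 9.2 collects "date of the procedure, time of first injection of the mixture". The choice matters most for subjects who consent on the procedure day. By date none of their AEs is lost; by clock time their whole pre-injection period is.

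**4. Size per subject.** A subject whose only procedure-related AE falls in the uncounted period lowers the percentage with such an AE by 1/125 = 0.8 points if 125 are treated. If 100 are treated (an assumption, taken from the minimum mentioned in Protocol 1), it is 1/100 = 1.0 point. A subject with another procedure-related AE inside the window changes only the event count.

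**The case against.** The strongest reply is that the omission is deliberate. SAP 2.3.2 describes a set of AEs and does not promise a table from consent; 5.6.2.4 openly assigns pre-procedure AEs to listings; Protocol 12.3 names only the procedure and follow-up periods; and the objectives concern the mixture. SAP 5.6.1 even measures procedure duration from the first injection, and Protocol 9.2 collects no puncture time. A one-line rule that the widest window opens on the date of the first procedure would count the same-day events without any new table.

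Much of this stands. It explains most of the gap before the procedure day and keeps the point minor. Three things remain. Protocol 12.3 plans numbers and percentages for the AE criterion, which a listing does not supply. Neither 12.3 nor the duration formula in 5.6.1 says that AEs of a procedure begin only at injection. And a date rule would still leave the days between consent and procedure uncounted, so the criterion as defined would still have no table.

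Stronger readings are tempting, but the documents do not support them:

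- That same-day pre-injection events are certainly dropped: this depends on the unstated rule.
- That pre-injection events at a second procedure are lost too: the widest window counts them.
- That safety data go missing: all AEs, and deaths and serious AEs separately, are listed.
- That enrolled but uninjected subjects are wrongly left out of the tables: Protocol 12.1 assigns all safety parameters to the Treated Set, and their AEs are still listed.
- That the SAP has no such table anywhere: sections 4 and 6 cannot be seen.

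**Conclusion.** The mismatch is real and minor. As visible, SAP 5.6.2.4 does not tabulate the AE criterion that SAP 2.3.2 and Protocol 7.2 define. AEs between consent and the first procedure are listed and not counted. Under a clock-time rule, procedure-related AEs before the first injection of the first procedure also go uncounted.

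How many events are affected cannot be estimated from the documents; the 0.8 points per affected subject assumes that all 125 required subjects are treated. The primary criterion, the ADR windows, the AE and serious AE listings and the quarterly board review (SAP 3.6) do not change. The conclusion assumes that the unseen SAP sections hold no overall AE table.

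**What to change.** In SAP 5.6.2.4:

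1. Add one overall table on the Treated Set from ICF signature to the end of follow-up, with subjects and events for any AE, any serious AE, and AEs related to the study procedure.
2. State whether the existing window from first administration uses onset date or clock time. Clock time need not be imposed once the new table exists, because that table counts the same-day events either way.
3. In the new table, extend the missing-relationship exception of SAP 5.6.2 to procedure relatedness. The exception for onset before the first procedure date now covers the mixture only, so a pre-procedure AE with missing relationship would be counted as procedure-related.

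The existing tables and ADR windows stay as they are. The cost is SAP wording, one short table from data already collected, and a footnote on why its counts may be slightly higher than those in the first-administration table. The full template of 20 summary parameters and 7 SOC/PT distributions used for the other windows is not needed.
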